3.3 Estimands and Intercurrent Events

A composite variable strategy will be used to address intercurrent events (ICH E9(R1), 2019). In the B3SHORT trial, the relevant intercurrent event is death. Under the composite variable strategy, patients who die without a measurement of the outcome, and when death is informative of the outcome, will be given a value of the outcome variable that reflects that they are dead. This applies to some of the secondary outcomes. The precise definition of how this will be handled for each outcome will be given in Section 6 (Statistical Analysis Methods) under the Missing Data section.

3.4 Analysis Populations

The Enrolled set will include all patients who have provided informed consent and have been included into the study data base.

The Full Analysis Set (FAS) will be defined as all patients randomly assigned to a treatment group having received at least one dose of study medication.

The Safety Analysis Set (SAS) will include all patients having received at least one study medication. Subjects who withdraw from the study will be included in the SAS. A list of withdrawn subjects, with the reasons for withdrawal, will be made.

The Per Protocol Analysis Set (PPS) will include all randomised patients meeting the study eligibility criteria, with no major protocol deviations affecting the treatment efficacy, and who are compliant for the study drug.

4 Trial Population

4.1 Screening Data, Eligibility and Recruitment

The total number of screened patients and reasons for not entering the trial will be summarized and tabulated.

A CONSORT flow diagram will be used to summarize the number of patients who were:

- assessed for eligibility at screening (estimate only)
- eligible at screening (estimate only)
- eligible and randomised
- received the randomised allocation
- did not receive the randomised allocation*
- discontinued the intervention
- randomised and included in the primary analysis
- randomised and excluded from the primary analysis*

4.2 Withdrawal/Follow-up

The status of eligible and randomised patients at trial end will be tabulated by treatment group according to

- Completed intervention and assessments to the primary endpoint (discharge from hospital)
- completed intervention and assessments
- completed assessments but not intervention
- Withdrew (with reason)
- lost to follow-up

^{*}reasons will be provided.

4.3 Baseline Patient Characteristics

 The patient demographics and baseline characteristics to be summarized include age in years, gender, ethnicity, body mass index, type of accommodation/level of care before admission, smoking status, level of frailty, Charlston score, in-hospital level of care, type of treatment during hospital stay (pressor, respiratory support, 02 supply), diagnosis, SAPSscore, degree of inflammation (highest CRP), mortality and morbidity (number of new organ failures).

Patient demographics and baseline characteristics will be summarized by randomised treatment arm and overall using descriptive statistics for continuous variables, and number and percentages of patients for categorical variables. There will be no statistical analysis of treatment difference. Any clinical important imbalance between the treatment groups will be noted.

5 Definitions of endpoints and Other Variables of Interest

Primary endpoint

Length of Hospital Stay

The length of hospital stay is defined as the number of days from commencing study treatment to medically fit for discharge from the hospital (to home, long term care facility or rehabilitation center or other facility with a lower care level). The term "Medically fit for discharge" is used instead of "discharge" to correct for extended stays due to logistical challenges (Example: medically fit for discharge, but no availability in long term facilities at that time). Only one patient was not discharged on the same day as she/he was medically fit for discharge). Admission to other hospitals after transfer from the first will be included in the total length of stay. The primary outcome will be the time from start of study treatment to discharge. Patients who die before discharge will be censored at the time of death.

Secondary endpoints (safety)

All-cause Mortality

All-cause mortality is a time to event outcome, with the date of randomization as the time when a patient becomes at risk. If a patient does not die during the study's follow-up, the observation is censored at the patient's last automated follow up.

New Infections

New infections is defined as any infection, mild or serious, occurring between the last point of contact to the next i.e. if a patient has an upper airway infection after discharge, but before the 90 day follow up appointment, this will count as one new infection at the 90 day follow up appointment. The outcome will be the number of new infections per patient, which is a discrete numerical variable.

Re-admissions

Re-admissions is defined as number of all-cause hospital admissions, surgical and medical, up until end of study. The outcome will be the number of new admissions per patient, which is a discrete numerical variable.

Other variables of interest

Metabolites

Rise in NR metabolites from inclusion to day 7 (or discharge if discharged prior to day 7) and until day 90.

Table 1: Overview of outcomes to be reported in the main article. Outcomes to be presented in subsequent articles are listed and defined in the protocol but not shown here.

Level	Outcome	Timeframe	Туре
Primary	Length of hospital stay (to medical fit for discharge)	65 weeks	Time to event
Secondary	Change in grip strength	90 days	Continuous (change from baseline)
	Change in grip strength	7 days	Continuous (change from baseline)
	All-cause mortality	-	Time to event
	Number of new infections per patient	65 weeks	Discrete numerical
	Number of re-admissions per patient	65 weeks	Discrete numerical

6 Statistical Analysis Methods

The overall statistical approach is presented in Section 2.4 and involves 1-3 steps of hypothesis testing and/or estimation of treatment effect. In step 1, only the patients in the normal dose group of NR will be used (in addition to the patients in the placebo group); in Step 2, only the patients in the medium dose group will be used; and in step 3, only the patients in the low dose group will be used. This approach will be followed for the primary and all secondary outcomes. The statistical methods for steps 1-3 will be presented for each type of outcome in the following subsections.

As an exploratory analysis, we will also perform an overall vs. placebo analysis, where the low, medium, and normal dose groups are combined and compared with placebo.

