2.6 Timing of Final Analysis

The main analysis is planned to after patients have concluded 90 days of treatment and attended the 65 weeks follow-up appointment. All data will be entered, verified and validated before the primary database will be locked, un-blinded and data analysis commenced.

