2.7 Timing of Outcome Assessments

The target days and visits windows are defined in the protocol as:

Target Day	Definition (Day window)	
-14	Two weeks prior to acute	
	admission to hospital	
Day 1 (Randomization)	Day 1	
Day 3	Target day -1 day/+2 days	
Day 7, 14, 21, 28	Target day± 3 days	
Day 30	Target Day ±10 days	
Day X	Discharge date ± 0 days	
Day X	Withdrawal date ± 0 days	
Day X	Death date ± 0 days	
Day 90	Target day + 90 days/-30days.	
65 weeks	Target day +/-180 days.	
	-14 Day 1 (Randomization) Day 3 Day 7, 14, 21, 28 Day 30 Day X Day X Day X Day X Day 90	

3 Statistical Principles

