6.4 Secondary Discrete Numerical Outcomes

The secondary discrete numerical outcomes are number of new infections per patient and number of re-admissions per patient. Both outcomes are measured as a count from 0 to the maximal number of events (new infections or re-admissions). We expect the maximal numbers of events to be at most 10. The analyses will be performed on the FAS.

Statistical Method for Steps 1-3

The mean number of events per patient will be compared between the NR and placebo groups – in each of the three steps – with a two-sample T test with adjustment for unequal variances (Fagerland et al., 2011).

Presentation of Results

The observed number and percentages in each treatment group in each category (0, 1, 2, ..., max number of events) will be presented together with the observed mean values and standard deviations in each treatment group and the estimated treatment difference with a 95% confidence interval.

Missing Data

If a patient has died, we will impute the missing data with the 80th percentile for the variable of interest (based on all patients regardless of treatment group). In cases where the 80th percentile= 0, the maximum number of events will be used.

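### Infection counts, and possibly re-admission counts, cover unequal follow-up that the planned comparison of means ignores

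*SAP*

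**What the plan says.** SAP Section 5 defines both outcomes, and their counting periods are set differently.

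- **New infections** are those "occurring between the last point of contact to the next". The last interval therefore closes when the patient is last seen.
- **Re-admissions:** "Re-admissions is defined as number of all-cause hospital admissions, surgical and medical, up until end of study". The variable is a plain count: "The outcome will be the number of new admissions per patient, which is a discrete numerical variable".
- **Outcome table (SAP Section 5):** both counts have a timeframe of 65 weeks. No text says that later events are dropped, or that patients seen earlier are followed up to that day.
- **Visit window (SAP 2.7):** for the 65-week visit it is "Target day +/-180 days". SAP 2.6 places the main analysis after patients have "attended the 65 weeks follow-up appointment".
- **Analysis (SAP 6.4):** "The mean number of events per patient will be compared between the NR and placebo groups" in each step, "with a two-sample T test with adjustment for unequal variances". There is no rate, offset or person-time.
- **Incomplete follow-up (SAP 6.4):** the only rule is "If a patient has died, we will impute the missing data with the 80th percentile for the variable of interest", or with the maximum if that percentile is zero.
- **Role of the result (SAP 2.4):** secondary outcomes are estimated, not tested, but steps 2 and 3 are carried out only if the preceding 95% confidence interval excludes the null value.

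The protocol bears on this in three places. Section 6.2.5 collects re-admissions from hospital charts. Section 6.3.1 follows withdrawn patients at discontinuation and at the end of the study. The end-of-study label is attached to a visit at about 65 weeks in Table 2 of Section 6.1, but to day 90 in Section 8.4.

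**The concern.** A raw count grows with the time over which it is collected. For infections, a patient seen late contributes more time than one seen early, and the t test treats the two alike. For re-admissions the same happens if the counting period ends at the visit, and the SAP does not say whether it does. SAP 4.2 expects some patients to withdraw or be lost, and Section 3.4 keeps them in the full analysis set once dosed, but no rule covers their shortened infection counts.

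Visit timing that varies equally in all groups costs precision only. The risk of bias comes from the design. Each dose was given in one phase (SAP 2.1), whereas every step uses placebo patients from all three phases (SAP Section 6). Randomization within a phase therefore does not balance visit timing in these comparisons. If one phase had later visits, its dose group would appear to have more infections; with earlier visits it would appear safer than it is. The SAP lists both outcomes under safety and reports them in the main article.

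**Working it through.** **Inputs from the documents.** Target 65 weeks, window 180 days either side (SAP 2.7); step 1 compares 20 patients on the normal dose with 18 on placebo, 6 from each phase (SAP 2.1 and Section 6).

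**Assumptions.** The documents give no event rate, only an expected maximum of 10 events, and no visit dates. I assume 0.5, 1 or 2 events per year, constant over time.

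**1. Observation window.**
- 65 × 7 = 455 days.
- 455 − 180 = 275 and 455 + 180 = 635.
- 635 / 275 = 2.31.

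**2. Expected count for one patient** = rate × days / 365.25.

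| Rate per year | Day 275 | Day 455 | Day 635 |
|---|---|---|---|
| 0.5 | 0.38 | 0.62 | 0.87 |
| 1 | 0.75 | 1.25 | 1.74 |
| 2 | 1.51 | 2.49 | 3.48 |

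**3. A moderate timing difference between groups.** Suppose a dose group is seen on average at day 500 or 550 and pooled placebo at day 455.
- Ratio of expected counts with no NR effect: 500/455 = 1.10; 550/455 = 1.21.
- Spurious difference at 1 event per year: 45/365.25 = 0.12; 95/365.25 = 0.26.

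**4. How far the phases must differ to produce this.** One third of placebo (6 of 18) belongs to the same phase as the dose group. If timing depends on phase alone and the other two phases average day x:
- (550 + 2x)/3 = 455 gives x = 407.5, so the phases differ by 550 − 407.5 = 142.5 days.
- (500 + 2x)/3 = 455 gives x = 432.5, so the phases differ by 67.5 days.

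In general the gap between phases must be 1.5 times the gap that reaches the comparison.

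**5. Effect on the planned interval.** I simulated the unequal-variance t interval, 20 v 18, with no true rate difference. Counts were Poisson or overdispersed (gamma-Poisson, dispersion 1). The entries show how often the 95% interval excludes zero at 1 event per year.

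| Mean timing difference | Visit spread assumed | Poisson to overdispersed |
|---|---|---|
| 45 days | SD 50 days | 5–6% |
| 95 days | SD 50 days | 6–10% |
| 60 days | uniform in window | 7.1% to 5.6% |
| 120 days | uniform in window | 14.1% to 8.4% |
| 180 days | uniform in window | 25.8% to 13.5% |

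With no timing difference the figure is 4–5%, whichever spread is assumed. At 45 to 95 days the spurious difference of 0.12 to 0.26 compares with an interval half-width of about 0.7 to 1.1 events. At 2 events per year with Poisson counts, a 95-day difference gives about 15%. By step 4, the 180-day row needs a gap between phases of 1.5 × 180 = 270 days.

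**6. With the counting period fixed.** Cutting every patient's count at one common day (275 in the simulation, so that all are fully observed) gives 4.1% to 5.0% in every scenario.

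**The case against.** The strongest reply is that 65 weeks in the outcome table already is a fixed period, and that re-admissions come from hospital charts, so neither an early visit nor withdrawal from treatment by itself ends their ascertainment. For re-admissions this largely stands. What is left is an ambiguity: the definition runs to the end of the study, that label is used for two different times, and no sentence makes 65 weeks a cut-off. A reader might infer that re-admission counts demonstrably stop at the visit; no passage says so. For infections the reply fails, because the definition is tied to contacts.

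A second reply is that the window is an outer tolerance and that nothing shows timing to differ by group. This stands too. The protocol's June 2023 amendments mention delay from the pandemic and a heavy workload, which makes drift between phases conceivable, but that is not evidence about visit dates. The 6 concurrent placebo patients in each phase also dampen any drift.

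Third, SAP 2.4 makes all analyses other than the primary supportive or exploratory, and tests hypotheses only for the primary outcome. That limits the consequence but does not remove it, since these intervals decide whether the lower doses are estimated at all.

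**Conclusion.** The point holds as a defect of method for infections and as an unclear counting period for re-admissions. Followed as written, SAP 6.4 compares infection counts over periods that may differ 2.31-fold between patients, with no allowance for visit timing or withdrawal.

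The certain cost is some added noise. Bias is conditional: it needs visit timing to differ between a dose group and pooled placebo. One might be tempted to conclude that the dose comparisons are confounded by follow-up time. The documents do not support that, since they give no visit dates. Under the assumed 45- to 95-day difference and 1 event per year, the distortion is 0.12 to 0.26 events per patient, and the interval wrongly excludes zero in 5–10% of trials instead of 4–5%. The larger figures need gaps between phases or event rates that nothing in the documents suggests.

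All these sizes assume a constant event rate. If infections become rarer as patients recover, the extra late days matter less. The correction should be made because it is cheap and removes a dependence on visit timing; the primary analysis is not affected.

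**What to change.** 1. **Re-admissions.** Count only admissions from start of treatment to day 455 for every patient, taken from hospital charts whatever the date of the visit. The t test and the rule for deaths can stay.
2. **Infections.** Analyse all patients in one rate model, named in advance (for example negative binomial, or Poisson with robust standard errors), with the log of actual follow-up time as offset. Follow-up runs to last contact, withdrawal or death. Cap both count and time at day 455 where onset dates allow. Protocol 8.4 describes standard adverse-event collection only to 30 days after day 90, so later onset dates may be incomplete; where they are, carry both count and time to the last contact.
3. **Deaths in the infection analysis.** Use the observed count and observed time. An imputed 80th percentile over a short follow-up would inflate the rate, so keep that imputation with the t test as a sensitivity analysis.
4. **Reporting.** Tabulate follow-up time by dose group and placebo, so that readers can see whether timing differed.

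The cost is SAP wording and some work on event dates. Events after day 455 leave the main re-admission count, and the main infection count where the cap applies. The infection result becomes a rate ratio rather than a difference in means. The offset corrects fully only if the rate is roughly constant over follow-up, which is a reason to apply the cap where dates permit.

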#### 5.2 Dosage and Administration

The capsules are taken orally and contain 250 mg of NR or placebo. Placebo or NR capsules will be administered after randomization as described below. (Please also see flow chart under point 5).

- First 16 patients enrolled: 1 capsule 250 mg every morning.
- Following 16 patients enrolled: 1 capsule of 250 mg morning and evening for three months.

- Following 26 patients enrolled: 2 capsules of 250 mg morning and evening for three months.
- High dose of 1000 mg morning and evening has now been cancelled (12.06.2023)

During hospitalizations the capsules will be administered by the hospital personnel while the capsules will be self-administered after discharge. Three months of NR or placebo will be released to the patient at randomization.

The capsules should ideally be swallowed whole, but if necessary, they may be opened before administration and the content poured into a small amount of water for administration in PEG/nasogastric tube. The content should not be chewed or crushed. The absorption of True Niagen remains the same if administered in this fashion, but unusual administration methods will be registered. The capsules may be opened by the hospital staff, but not by the study staff.

Due to strict inclusion criteria, and the expected frailty level of such patients, it is unlikely that two included patients will meet. It is thus unlikely that opening the capsules will lead to patient un-blinding.

A missed dose should be taken as soon as possible, but not any later than 6 hours after the usual time. If more than 6 hours have passed, the patient should wait until the next dose is scheduled.

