2.2 Randomization

Eligible patients are allocated in a 5:3 (phases 1 and 2) or 10:3 (phase 3) ratio between NR and placebo, using a computer randomization procedure. The randomization is blocked within each phase. Details of block size and allocation sequence generation is provided in a separate document unavailable to those who enroll patients or assign treatment.

Details of the randomization including the final random allocation list are held securely and unavailable to unauthorized trial personnel.

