2.3 Sample size

Assuming the time of hospitalization after randomization follows a Weibull distribution with a scale parameter λ = 18 and shape parameter κ =2.2 (corresponding to a median of 15 and an IQR of 10 – 21), we need to include 58 patients: 18 in the placebo group, 10 in the 250 mg/day group, 10 in the 500 mg/day group, and 20 in the 1 g/day group) in order to reach approximately 80% power to show a significant dose-response in this study with a maximal reduction in time of hospitalization of 33%. This calculation is based on optimal designs in dose-finding studies according to the MCPMod methodology with three alternative dose-response curves: linear, e-max and exponential (Pinheiro et al., 2014).

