6.1 Primary Outcome

The primary outcome is length of hospital stay (time to discharge), measured in number of days, and the primary analysis of the primary outcome will be performed on the full analysis set (FAS). A secondary (sensitivity) analysis of the primary outcome will be performed on the per protocol set (PPS).

Statistical Method for Steps 1-3

The comparison of the length of hospital stay between the NR and placebo groups – in each of the three steps – will be carried out with a Weibull survival model, with time as the number of days of hospital stay and treatment (NR vs placebo) as explanatory variable. The estimated treatment effect will be the hazard ratio (HR) for treatment with a 95% confidence interval.

Presentation of Results

The estimated treatment effect (HR) with a 95% confidence interval will be presented, together with the P-value for the null hypothesis of a zero-treatment difference (HR = 1).

The observed mean and standard deviation for placebo and each dose will be presented in a figure, along with the observed values (length of hospital stay) for each individual, as a scatter with connected lines-plot. Figure 1 shows an example with simulated data.

A plot of the Kaplan-Meier survivor function (for time to discharge) of each dose and placebo will be presented.

[figure not shown]

Figure 1: Simulated data

Missing Data

We will have complete data on the length of hospital stay, except for the following situation: A patient dies before being discharged from the hospital. In this case, the patient will be censored at the time of death. Imputation of the length of hospital stay will be performed as a sensitivity analyses (see item 3 below).

Sensitivity Analyses

The following sensitivity analyses will be performed on the primary outcome:

- 1. As described above but on the per protocol set (PPS)
- 2. As described above but with Cox proportional hazard regression instead of Weibull regression
- As described above but with Cox proportional hazard regression and imputation (instead of censoring) of the length of hospital stay with the maximum length of hospital stay (regardless of treatment group) for patients who die before discharge

Subgroup Analyses

There will be no subgroup analyses.

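### The exploratory overall NR v placebo analysis pools three phases with different allocation ratios and should be stratified by phase

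*SAP*

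**What the plan says.** **Design.** SAP 2.2: "Eligible patients are allocated in a 5:3 (phases 1 and 2) or 10:3 (phase 3) ratio between NR and placebo", blocked within each phase. SAP 2.3 sets the groups at "18 in the placebo group, 10 in the 250 mg/day group, 10 in the 500 mg/day group, and 20 in the 1 g/day group". SAP Table 1 shows six placebo patients in every phase. The phases are successive: Protocol 5.2 assigns the first 16 patients to one regimen, the next 16 to another, and then "Following 26 patients enrolled: 2 capsules of 250 mg morning and evening for three months".

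**Analysis.** The opening text of SAP section 6 adds an exploratory comparison "where the low, medium, and normal dose groups are combined and compared with placebo". It gives no model for it. The models that are written, each for steps 1 to 3, are:

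- a Weibull model with "treatment (NR vs placebo) as explanatory variable" (6.1)
- a mixed model with treatment, time and their interaction (6.2)
- a Cox model with treatment only (6.3)
- a two-sample t test (6.4)

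Phase is not a covariate or stratum in any of them, nor in the protocol's outline of the analysis.

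**The concern.** Patients were randomised within phase, and the NR share differs by phase: 10/16 = 62.5%, 10/16 = 62.5% and 20/26 = 76.9%. When the phases are merged and phase is ignored, phase becomes a possible confounder through the design alone, although each phase is soundly randomised.

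The documents give reasons why stays might drift. Recruitment could widen to other wards or hospitals (Protocol 4.1), the liver criterion was relaxed (Protocol 4.4 and Amendment 1), and the pandemic slowed the project (June 2023 amendments).

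This is the only planned comparison that uses all 58 patients, and every NR patient in it has concurrent placebo patients from the same phase. If step 1 of the primary procedure fails, formal testing stops and readers will look to the pooled result. SAP 3.1 labels any P-value below 0.05 statistically significant and makes no exception for exploratory analyses.

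**Working it through.** **Inputs.** Group sizes by phase: NR 10, 10, 20 and placebo 6, 6, 6 (SAP Table 1). Stay: "Weibull distribution with a scale parameter λ = 18 and shape parameter κ =2.2" (SAP 2.3). Effect: "maximal reduction in time of hospitalization of 33" per cent (SAP 2.3), a time ratio of 0.67. Two-sided 5% level (SAP 2.4 and 3.1). Assumed because the documents give no value: the ratio r of phase 3 stays to phase 1 and 2 stays, no deaths or dropout, and the parameters of the dose-response curves.

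**1. The plan's own figures.** Weibull quantile = 18 × (−ln(1−p))^(1/2.2). This gives a median of 15.2 and quartiles of 10.2 and 20.9, as stated. For the power, I used MCPMod on log stay, with the SE of a contrast = (1/2.2) × √(Σc²/n) and one-sided 0.025. It gives 78% (linear), 77% (e-max, ED50 250 mg assumed) and 84% (exponential, delta 250 mg assumed), mean 80%. The stated 80% is reproduced, but it belongs to the dose-response test. No power is stated for the pooled comparison.

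**2. The leak.** The phase mix is 1/4, 1/4, 1/2 in NR and 1/3, 1/3, 1/3 in placebo. With d₁, d₂, d₃ the phase levels of mean log stay:

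bias = (1/4 − 1/3)d₁ + (1/4 − 1/3)d₂ + (1/2 − 1/3)d₃ = (1/6) × [d₃ − (d₁ + d₂)/2]

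For r = 1.5 this is ln(1.5)/6 = 0.405/6 = 0.068. The planned log effect is |ln 0.67| = 0.400, so 0.068/0.400 = 17% of it is lost. In simulation the mean time ratio moves from 0.676 to 0.722.

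**3. Power.** Simulated 58-patient trials in the 10:6, 10:6, 20:6 layout, Weibull regression, Wald test on the log hazard ratio, equal 33% reduction at every dose:

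| Phase 3 stays | Treatment only | With phase |
|---|---|---|
| no difference | 85% | 84% |
| +10% | 81% | 84% |
| +25% | 75% | 84% |
| +50% | 63% | 84% |

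Repeat runs moved single entries by up to about 3 points and left the pattern unchanged.

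Other curves at +50%: e-max (ED50 250 mg assumed) 54% v 69%, a loss of 15 points. Linear: a loss of about 5 to 6 points, from pooled power of only about 46% with phase in the model.

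**4. No NR effect.** Two-sided rejection by the treatment-only model is 5.9% with no gap and 8.3% to 8.6% at +50%. At r = 0.67, false findings that NR shortens stay are 5.2% to 5.4% without phase and 2.5% to 2.9% with it.

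**5. Grip strength.** The quantity of interest is the treatment-by-time contrast. In complete simulated data where change differed by phase, adding phase indicators alone left it untouched (2.1387, SE 1.365, both ways). Adding phase-by-time moved it to 0.87.

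**The case against.** The analysis is exploratory. SAP 2.4 names a single primary analysis, and the pooled result enters no decision rule. The SAP does not write the pooled model, so a treatment-only form is an inference from 6.1 to 6.4. All of this stands and keeps the stakes low. It also means that the model still has to be specified.

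A reader might go further in three ways that the documents do not support:

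- **That any difference between phases biases the result.** Only a gap between phase 3 and the average of phases 1 and 2 does, and one sixth of it. A phase 1 v phase 2 difference with phase 3 midway gives no bias on the log scale, although the extra spread still costs about 8 points of power at ±50% with equal dose effects.
- **That more than 20 points of power are at stake as a matter of course.** That needs phase 3 stays about 50% longer together with the same reduction at every dose. The SAP describes 33% as the maximal reduction and plans for linear, e-max and exponential curves, so a flat effect is not its planning case.
- **That power is always lost.** With shorter phase 3 stays and equal dose effects, the treatment-only model rejects more often (90% v 84% at −25%). The harm there is false positives.

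The same omission bears harder on primary step 1, where all 20 patients on 1 g/day but only 6 of 18 placebo patients are from phase 3, so that 1 − 1/3 = two thirds of a gap would enter. There most of the placebo group is non-concurrent and adjustment costs much more. That is a separate question, and the fix below does not settle it.

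**Conclusion.** The point holds as a cheap improvement to an exploratory analysis. The unequal phase mix is a fact of the design, and no written method accounts for it. Whether it matters depends on a phase difference that the documents neither report nor predict. With equal 33% effects, the loss is about 1 to 3 points at +10%, 9 at +25% and 21 at +50%. It is about 5 points at +50% under a linear curve. With phase 3 stays at 0.67 times the others, the one-sided false-positive rate roughly doubles, from 2.5% to about 5%. These figures assume a common Weibull shape of 2.2 and no deaths or dropout. Nothing here shows that the trial's pooled result is biased, and the primary decision rule is unaffected.

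**What to change.** State in SAP section 6 that the overall NR v placebo analysis is stratified by randomisation phase:

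- **Length of stay:** phase indicators in the Weibull model, and a Cox model stratified by phase in the sensitivity analyses.
- **Grip strength:** phase and phase-by-time terms in the mixed model, since phase alone does not adjust change from baseline.
- **Mortality:** a Cox model stratified by phase.
- **Infections and re-admissions:** a phase-stratified mean difference.

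Add that, because each dose was given in one phase only, the result is a weighted average of three within-phase comparisons.

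**Cost.** A few lines of text. If phases do not differ, the price for length of stay is about 1 to 2 points of power (85% to 84% with equal effects, 72% to 70% under e-max). The cost for mortality was not worked out, and that model has only six placebo patients per stratum. Protocol 10.4 allows changes to the plan until database lock. The choice should be fixed before unblinding.
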